8.2.15. Allergic Rhinitis Visual Analog Scale (AR-VAS)

The AR-VAS score will be summarized at each post-baseline visit (Week 12 and Week 24).

In addition, at each post-baseline visit until Week 12, the change from baseline will be modelled using the same MMRM model used for the analysis of the primary endpoint. LS mean difference between the dupilumab and placebo group, the corresponding 95% CI of the difference and two-sided p-values will be provided. All p-values except for Week 12 will be considered nominal.

8.2.16. Psychomotor Vigilance Test (PVT)

The PVT variables, total errors, number of lapses, mean reciprocal response time, mean fastest response time, and mean slowest reciprocal response time will be summarized at each post-baseline visit (Week 12 and Week 24).

In addition, at each post-baseline visit until Week 12, the change from baseline will be modelled using the same MMRM model used for the analysis of the primary endpoint. LS mean difference between the dupilumab and placebo group, the corresponding 95% CI of the difference and two-sided p-values will be provided. All p-values except for Week 12 will be considered nominal.

For tests that indicate “Failed QC: clear non-compliance”, the tests and the associated metrics will be excluded from the analyses since the results are judged to be procedurally non-compliant rather than due to psychomotor impairment. If the difference in the proportion of “Failed QC: clear non-compliance” tests

between the treatments is more than 20 %, an exploratory analysis of the summaries mentioned above will be repeated by including these tests.

8.2.17. Neurocognitive Test (Automated Neuropsychological Assessment Metrics [ANAM])

The ANAM variables, mean response time for all responses, percentage of correct response and throughput will be summarized at each post-baseline visit (Week 12 and Week 24) and for each of the three substests.

In addition, at each post-baseline visit until Week 12, the change from baseline will be modelled using the same MMRM model used for the analysis of the primary endpoint. LS mean difference between the dupilumab and placebo group, the corresponding 95% CI of the difference and two-sided p-values will be provided. All p-values except for Week 12 will be considered nominal.

For tests with validity flag as “Invalid”, the tests and the associated metrics will be excluded from the ANAM data analysis. If the difference in proportion of “invalid” tests between the treatments is more than 20%, an exploratory analysis of the summaries mentioned above will be repeated by including these tests.

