The table below summarizes recommended usage of results in the analyses for all combinations. Per these rules, if a patient has both a “1” (first test) and a “0” (retest) on the same visit, only the “0” (retest) should be included in the analysis.

Table 15.9.1 Recommended usage of results in the analyses for all combinations

First Test	Retest Test	Primary Analysis Approach	Sensitivity Analysis Approach
------------	-------------	---------------------------	-------------------------------

NO RETEST PROCESS IMPLEMENTED			
(0) No Flag	-	Include	(same as primary analysis)
(1) Ambiguous Compliance Flag	-	Include	(same as primary analysis)
(2) Clear Non-Compliance Flag	-	Exclude	Include
AFTER RETEST PROCESS IMPLEMENTED			
(0) No Flag	-	Include first	(same as primary analysis)
(1) Ambiguous Compliance Flag	(0) No Flag	Exclude first, include retest	(same as primary analysis)
	(1) Ambiguous Compliance Flag	Exclude first, include retest	(same as primary analysis)
	(2) Clear Non-Compliance Flag	Include first, exclude retest	(same as primary analysis)
(2) Clear Non-Compliance Flag	(0) No Flag	Exclude first, include retest	(same as primary analysis)
	(1) Ambiguous Compliance Flag	Exclude first, include retest	(same as primary analysis)
	(2) Clear Non-Compliance Flag	Exclude first, exclude retest	Exclude first, include retest

If a subject has multiple retests performed, the above process will be performed for all the retests in chronological order i.e. first retest will be compared to second retest, etc...

Neurocognitive Test

The ANAM tests are administered by a computer/iPad/electronic device and patients need only to use the 2 mouse buttons to respond. For each of the tests, patients will be provided instructions that describe how to take the test and indicate a correct response. The ANAM comprises of three subsets:

- Running memory assesses sustained attention, working memory, and resistance to interference. The test requires sustained attention in response to a stimulus on the computer screen during a forced-pace, rapid task. Numbers are presented on the screen and the user must press a specified key indicating whether the number is the same as or different than the previous number. The subtest takes approximately 5 minutes to complete.

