- Mathematical processing assesses mathematical computation and working memory. The test involves Math problems being presented on the screen. The answer must be figured out then the user must decide if the answer is > or < the number 4. The subtest takes approximately 5 minutes to complete
- Procedural reaction time is an assessment of choice reaction time. The user must tap the left button if the number shown on the screen is 2 or 3 and the right mouse button if the number shown on the screen is 4 or 5. The subtest takes approximately 3 minutes to complete.

ANAM test scores will be reviewed periodically by Vista Life Sciences and Washington Neuropsychology Research Group, LLC (WNRG) to identify atypical observations or those that are indicative of invalid performance. Accuracy scores $\leq 56\%$ will be identified and flagged as "Invalid".

The tests included in the Dupistad Study battery are not overly difficult. In addition, they all involve binary response options, thus 50% accuracy would reflect chance-level responding. Tests with validity flag as “Invalid” will be excluded from the ANAM data analysis. If the difference in proportion of “invalid” tests between the treatments is more than 20%, an exploratory analysis of the summaries in [section 8.2.17](#) will be repeated by including these tests.

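### ANAM tests are excluded on an accuracy score that is itself analysed, and the analysis that restores them depends on a loosely defined 20% trigger that can miss clear imbalances; the PVT sensitivity rules also need reconciling.

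*SAP*

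**What the plan says.** **ANAM.** SAP 8.2.17 analyses mean response time, percentage correct and throughput for each of three subtests, with a model-based comparison at Week 12. SAP 15.9.2 sets the validity rule: "Accuracy scores $\leq 56\%$ will be identified and flagged as" invalid, and invalid tests leave the analysis. The reason given is that the tasks are not overly difficult and "they all involve binary response options, thus 50% accuracy would reflect chance-level responding". The excluded tests come back only if the arms differ enough in the invalid proportion, under a clause that ends "tests between the treatments is more than 20%, an exploratory analysis of the summaries mentioned above will be repeated by including these tests".

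**PVT.** Under SAP 15.9.2 a quality check against pre-defined thresholds may lead to a retest. Tests that fail are reviewed by the vendor and discussed with site facilitators, and then receive one of three flags. For tests flagged as clearly non-compliant, the tests and "the associated metrics will be excluded from the analyses" (SAP 8.2.16). Tests of ambiguous compliance are kept unless a usable retest replaces them. Above the same 20% difference, "an exploratory analysis of the summaries mentioned above will be repeated by including these tests".

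**Table 15.9.1**, which covers PVT only, has a column headed "Sensitivity Analysis Approach" and states no condition. **Appendix 15.1** lists no supportive analysis for PVT and ANAM.

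**The concern.** For ANAM, the variable that decides whether a test is kept is also an outcome. The protocol includes these tests to detect neurocognitive consequences of poor sleep, so a very low accuracy score may mean lack of effort or may mean impairment. The SAP describes no facilitator discussion or retest for ANAM that would separate the two.

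If patients who still sleep badly on placebo fall below the cut-off more often, the worst placebo results are removed and a real benefit is understated. Imbalance the other way would flatter dupilumab. Response time and throughput from the same tests go too.

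The natural safeguard is an analysis with the invalid tests put back. Here it depends on a threshold that leaves open the scale (absolute or relative) and the unit (visit, subtest or pooled). For PVT the concern is narrower: two programmers following different parts of the SAP could deliver different outputs.

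**Working it through.** **Inputs from the documents**

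- Evaluable patients: 50 placebo, 100 dupilumab (SAP 4.1). About 201 randomised 2:1 gives 67 and 134.
- Trigger: a difference of more than 20% between arms (SAP 8.2.16, 8.2.17, 15.9.2).

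**Assumptions**

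- 20% means percentage points, with one test per patient.
- Invalid rates are not given. The counts below are illustrative, and the dupilumab rate is varied over 2%, 5% and 10%.

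**Step 1. Check the arm sizes against the plan's own figure.** For the primary endpoint (difference 25, SD 44), the standard error is 44 × √(1/50 + 1/100) = 7.62. Then 25/7.62 = 3.28 and power = Φ(3.28 − 1.96) = 0.907, which agrees with the stated 90%. The plan gives no operating figure for the trigger.

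**Step 2. Imbalances that do not fire the trigger** (Fisher exact, two-sided)

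| Placebo | Dupilumab | Difference | p |
|---|---|---|---|
| 11/50 (22%) | 3/100 (3%) | 19 points | 0.0004 |
| 12/50 (24%) | 5/100 (5%) | 19 points | 0.0016 |
| 15/50 (30%) | 10/100 (10%) | 20 points, not above 20 | 0.0044 |
| 14/67 (20.9%) | 2/134 (1.5%) | 19.4 points | 0.000005 |

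**Step 3. How often the trigger fires.** With X ~ Bin(100, p) and Y ~ Bin(50, p + d), sum the joint probabilities over all outcomes where |Y/50 − X/100| > 0.20.

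| True imbalance d | p = 2% | p = 5% | p = 10% |
|---|---|---|---|
| 10 points | 0.02 | 0.03 | 0.05 |
| 15 points | 0.16 | 0.18 | 0.21 |
| 20 points | 0.46 | 0.46 | 0.47 |
| 25 points | 0.75 | 0.74 | 0.73 |

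**Step 4. Upper bound on the distortion.** Suppose the flagged tests are exactly the lowest scores of a normal outcome. Removing the lowest fraction q raises the mean by φ(z_q)/(1 − q) SD. For 2% v 12% excluded: 0.0484/0.98 = 0.049 and 0.2000/0.88 = 0.227, a spurious shift of 0.18 SD. For 5% v 20%: 0.1031/0.95 = 0.109 and 0.2800/0.80 = 0.350, a shift of 0.24 SD. The trigger would fire about 2% and 18% of the time in these two cases. For scale, the primary endpoint is powered for 25/44 = 0.57 SD.

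**Step 5. Unit of the proportion.** If tests were pooled over screening, baseline and Week 12, a 30-point imbalance confined to Week 12 would appear as 30/3 = 10 points. The SAP neither specifies nor excludes pooling.

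**Step 6. The PVT passages side by side**

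| Place | Analysis that includes clear non-compliance tests |
|---|---|
| SAP 8.2.16 | Only if arms differ by more than 20%; the failed tests are put back |
| SAP 15.9.2, text | Same condition, but counted on invalid tests, a term that is not one of the three PVT flags |
| Table 15.9.1 | Sensitivity column with no condition; if first test and retest both fail, only the retest enters |
| Appendix 15.1 | No supportive analysis |

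**The case against.** **The cut-off is reasonable.** On easy two-choice tasks, accuracy of 56% or less is close to guessing, and pre-specifying a validity rule is good practice. This stands as a defence of the primary rule. It does not show that every such score is lack of effort, which is what a routine sensitivity analysis would probe.

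**The counts are invented.** They are, and they were chosen to sit at or just below the threshold. Nothing in the documents suggests that 22% of placebo patients would perform near chance. The p-values show that imbalances far beyond chance can pass the trigger; they do not measure bias in the treatment estimate. On a relative reading of 20%, every example in Step 2 would fire it. That limits the numerical claim and adds to the case for removing an undefined condition.

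**Little depends on it.** PVT and ANAM are exploratory and outside the testing sequence in SAP 8.2.23. Applying the trigger also requires someone to compare invalid proportions by arm, so the imbalance would not go wholly unseen. Both points stand.

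**Two stronger readings are not supported.** A reader might infer that PVT tests, too, are excluded on their own result. The SAP describes a compliance judgement after review; the thresholds are not stated, so dependence on the result is possible but not shown. A reader might also infer that the trigger contradicts Table 15.9.1. That table does not cover ANAM. For PVT it can be read as saying which test to use if the analysis is run, so the passages are unreconciled rather than strictly contradictory.

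**Conclusion.** The point holds for ANAM: exclusion depends on an analysed outcome, and the only check is conditional on an incompletely defined threshold. If 20% means percentage points, the check misses 22% v 3% (p = 0.0004) and, with 50 v 100 tests and dupilumab invalid rates of 2-10%, fires about 46-47% of the time for a true 20-point imbalance and 2-5% for 10 points. These figures rest on assumed invalid rates, and the 0.18 to 0.24 SD shifts are upper bounds.

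For PVT the finding is an inconsistency between SAP 8.2.16, the text of 15.9.2, Table 15.9.1 and Appendix 15.1. The severity is low, because no confirmatory conclusion depends on either test.

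**What to change.** - Keep the primary exclusion rules for both tests.
- Delete the 20% condition in SAP 8.2.16, 8.2.17 and 15.9.2.
- Always run the sensitivity analysis: for ANAM, put the invalid tests back; for PVT, follow the sensitivity column of Table 15.9.1. A PVT analysis of every test would not match that table's retest rules.
- Report the number and proportion of excluded tests by arm and visit, and by subtest for ANAM.
- Change the PVT and ANAM row of Appendix 15.1 to list this sensitivity analysis.

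The cost is a few extra exploratory tables from data already collected.

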8.2.18. Polysomnography (PSG)

SE, TST, WASO, and SOL, all based on PSG measures, will be summarized at post-baseline visit (Week 12) on the PSG analysis set.

8.2.19. Work Productivity and Activity Impairment Questionnaire: Atopic Dermatitis (WPAI-AD)

The number and percentage of patients currently employed (yes/no) will be presented for each post-baseline visit (Week 4, Week 8, Week 12, and Week 24) alongside the number of patients evaluated at that visits

If employed, the number of hours missed due to AD in the past week, number of hours missed due to other reasons in the past week, number of hours actually worked in the past week, NRS of atopic dermatitis affecting productivity while working in the past week and NRS of atopic dermatitis affecting the ability to do regular daily activities other than work at a job in the past week will be summarized at each post-baseline visit (Week 4, Week 8, Week 12, and Week 24).

In addition, at each post-baseline visit until Week 12, the change from baseline will be modelled using the same MMRM model used for the analysis of the primary endpoint. LS mean difference between the dupilumab and placebo group, the corresponding 95% CI of the difference and two-sided p-values will be provided. All p-values except for Week 12 will be considered nominal.

8.2.20. Days missed from school or from work due to AD

The Days missed from school or from work will be summarized at each post-baseline visit (Week 4, Week 8, Week 12, Week 16, Week 20, and Week 24).

The total number of days of sick leave over 12 weeks will be analyzed using a negative binomial model, where days of sick leave through week 12 will be the response variable, the independent variables will be the treatment group and region, and the log transformation of duration of employment through week 12 will be used as the offset variable. No missing data will be imputed.

Sample code for negative binomial model:

```
proc genmod data = days_missed;  
class trt01pn region;
```

```
model aval = trt01pn region/ dist=negbin link=log offset=logdur;  
lsmeans trt01pn / pdiff cl exp;  
ods output lsmeandiffs=diffs lsmeans=lsmeans;  
run;
```

The duration of employment through week 12, days of sick leave through week 12 and employment duration adjusted sick leave days per 12 weeks will be summarized for each treatment group using descriptive statistics.

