4.2. Randomization, Stratification, and Blinding

Randomization will be stratified by: PSG (regardless of geographic location), non-PSG US, non-PSG Europe and non-PSG rest of world (ROW).

A participant who has been allocated to a randomized intervention regardless whether the intervention kit was used or not (ie, participant registered by the interactive response technology (IRT) will be considered a randomized subject). A participant cannot be randomized more than once in the study.

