6.1. Demographics

The following demographics and patient characteristics will be summarized by treatment group and overall:

- Age (years),
- Age categories (≥ 18 to < 40 , ≥ 40 to < 65 , ≥ 65),
- Gender (Male, Female)
- Ethnicity (Hispanic or Latino, Not Hispanic or Latino, Not Reported, Unknown),
- Race (American Indian or Alaska Native, Asian, Black or African American, Native Hawaiian or Other Pacific Islander, Multiple, White, Not Reported, Unknown),
- Baseline body weight (kg) with grouping (< 70 , ≥ 70 to < 100 , ≥ 100),
- Baseline height (cm),
- Baseline body mass index (BMI) (kg/m^2) derived as: $(\text{Weight in kg})/(\text{Height in meters})^2$,
- Baseline BMI categories (< 15 , ≥ 15 to < 25 , ≥ 25 to < 30 , ≥ 30)
- Region (US [PSG, non-PSG], Europe and ROW)
- Alcohol habits at screening (Never, Occasional, At Least Daily, At Least Weekly, At Least Monthly)

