6.2.3. Health economic endpoints at baseline

- WPAI-AD: currently employed status (yes/no); number of hours missed due to AD (only if employed); number of hours missed due to other reasons (only if employed); number of hours actually worked (only if employed); NRS of atopic dermatitis affected productivity while working (only if employed) and NRS of atopic dermatitis affected ability to do regular daily activities, other than work at job
- Day missed from school or from work due to AD : patients who were employed or enrolled in school were asked to report the number of sick leave/missed school days due to AD from each assessment since the last study visit, separately for employment/school status by full time and part time

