8.1.1. Primary Analysis

Percentage change from baseline in sleep quality NRS will be analyzed using a MMRM under the MAR framework. The MMRM model will include treatment (dupilumab, placebo), baseline value of sleep quality NRS, randomization stratum (region), visits (up to week 12), treatment by visit interaction, and baseline sleep quality NRS by visit interaction terms all as fixed effects. An unstructured correlation matrix will be used to model the within -patient errors. The Kenward-Roger approximation (**ddfm=kr**) will be used to estimate the denominator of degrees of freedom. Parameters will be estimated using restricted maximum likelihood method with the Newton-Raphson algorithm. LS mean difference between the dupilumab and placebo group, the corresponding 95% CI of the differences and 2-sided nominal p-values will be provided. The primary p-value is at Week 12. Any other p-values should be treated as suggestive for possible further study as the study is not powered for these tests.

If the number of patients in the PSG-sub study is less than 50% of planned, PSG-strata will be pooled with the non-PSG strata in the US and then there will be only 3 strata: US (combined non-PSG and PSG), Europe and ROW.

If the MMRM model fails to achieve convergence due to complexity of model specification, different covariance structures will be used according to the following order till convergence is achieved:

1. Unstructured correlation (UN)
2. Heterogeneous Toeplitz (TOEPH)
3. Homogeneous Toeplitz (TOEP)
4. First-Order Autoregressive [AR(1)]
5. Compound Symmetry (CS)

MMRM model will be built with the following sample SAS code to evaluate the treatment effect through week 12:

```
proc mixed data = adqs method = reml;
  where paramcd eq 'sleep quality NRS' and avisitn ge 2 and avisitn le 6 and ITTFL eq
  "Y";
  class usubjid stratum trt01pn avisitn;
  model pctchg = base trt01pn stratum avisitn trt01pn*avisitn base*avisitn / solution ddfm
  = kr;
  repeated avisitn / type = un subject = usubjid;
  lsmeans trt01pn*avisitn / cl;
  /*contrast "Dupilumab vs Placebo at Week 1 Visit 2"
    trt01pn -1 1 trt01pn*avisitn -1 0 0 0 0 1 0 0 0 0;
  contrast "Dupilumab vs Placebo at Week 2 Visit 3"
    trt01pn -1 1 trt01pn*avisitn 0 -1 0 0 0 0 1 0 0 0;
  contrast "Dupilumab vs Placebo at Week 4 Visit 4"
    trt01pn -1 1 trt01pn*avisitn 0 0 -1 0 0 0 0 1 0 0;
  contrast "Dupilumab vs Placebo at Week 8 Visit 5"
    trt01pn -1 1 trt01pn*avisitn 0 0 0 -1 0 0 0 0 1 0; */

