  ** 'x' should be code for the placebo group **
  model resp (event='1') = base trt01pn stratum avisitn avisitn*trt01pn base*avisitn /
    dist=binomial link=logit solution ddfm=kr;
  random _residual_ / subject=usubjid type=UN; ** type can also change here as in mixed
    to TOEPH, TOEP, AR(1) or CS to achieve convergence.**
  lsmeans trt01pn*avisitn / pdiff ilink OR CL;
run;
```

Note that sample code assumes that the relevant post-baseline visits until Week 12 are coded between 2 and 6 inclusive, if that is not the case, the code should be adjusted.

If the GLMM model fails to achieve convergence (even with simpler covariance structures), the responder variables will be analyzed using a logistic regression model, separately at each assessment time point through Week 12. The logistic regression model will include treatment (dupilumab, placebo) as fixed effect, and will include baseline value of EASI, randomization stratum (region) as fixed effect covariates. A summary table will present the estimated incidence for each treatment group and corresponding 95%

confidence interval (CI); also, the odds ratio, corresponding 95% CI and p-value for the treatment difference between the dupilumab and placebo group. An estimate of the odds ratio and a CI above 1 is an indication that you are more likely to be a responder on the active treatment group rather than placebo.

If the logistic regression model fails to achieve convergence at a post-baseline visit, the Clopper Pearson 95% CI of the incidence rate (expressed in percentage) and the 95% CI of the difference in incidence rate between treatment group and placebo (i.e. treatment – placebo) and p-value will be presented. The 95% CI for the difference between dupilumab and placebo will be based on the Cochran-Mantel-Haenszel (CMH) test adjusted by the randomization stratum, at the post-baseline time point.

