- Duration of employment through week 12 = sum of all employment intervals (specific assessment date – last assessment date) from the first visit till the last assessment of employment status on or prior to week 12 + 1 day. For the first post-baseline assessment, if no baseline assessment is recorded then randomization date should be used as last assessment date. Duration of employment will be calculated disregarding full or partial employment status.
- Days of sick leave through week 12 is the sum of all missed work/school days up to the last assessment date on or prior to week 12. For the first post-baseline assessment, if no baseline assessment is recorded and the number of missed days is higher than imputed employment duration then the number of missed days will be equal to employment duration.
- Employment duration adjusted sick leave days per 12 weeks will be used for treatment comparison. It is only applied for patients who are fully or partially employed. If days of sick leave through week 12 value is missing for a specific assessment, the length of this assessment interval will be deducted from the duration of employment through week 12.

Employment duration adjusted sick leave days per 12 weeks

$$= \frac{\text{Days of sick leave through week 12}}{\text{Duration (in days) of employment through week 12}} * 12 \text{ weeks (in days)}$$

Days missed from school or from work due to AD will be directly provided by KONEKSA.

Hospital Anxiety and Depression Scale (HADS)

The HADS is an instrument for assessing symptoms of anxiety and depression in non-[^]psychiatric populations; repeated administration also provides information about changes to a patient's emotional state. The HADS consists of 14 items, 7 each for anxiety and depression symptoms; possible scores range from 0 to 21 for each subscale.

The HADS scores will be directly provided by KONEKSA.

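### The missed work/school days model (SAP 8.2.20) includes no baseline measure of missed work, although two are scheduled at Week 0

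*SAP*

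**What the plan says.** SAP 8.2.20 models total missed days over 12 weeks with a negative binomial regression. The text says "the independent variables will be the treatment group and region", and the sample code matches it: "model aval = trt01pn region/ dist=negbin link=log offset=logdur". The offset is the log of employment duration through Week 12. Neither place has a baseline term.

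Two baseline measures of missed work are available:

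- **Missed days due to AD.** SAP 6.2.3 lists this among the baseline health economic variables: patients in work or school were "asked to report the number of sick leave/missed school days due to AD from each assessment since the last study visit". The schedule of activities (protocol 1.3, SAP 15.2) places it at Week 0.
- **WPAI-AD hours missed due to AD.** This is also scheduled at Week 0, has a 7-day recall, and is asked of employed patients only.

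SAP 8.2.19 analyses change in the WPAI-AD items with the primary-endpoint MMRM. In 8.1.1 that model contains the baseline value and "randomization stratum (region), visits (up to week 12), treatment by visit interaction".

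The outcome is derived in SAP 15.8: "Days of sick leave through week 12 is the sum of all missed work/school days up to the last assessment date" on or before Week 12. The sentence gives an end to the sum but no start.

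Missed days is an exploratory endpoint (protocol Section 3, SAP Table 3.1.1). It is not among the eight key secondary endpoints in SAP 8.2.23.

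**The concern.** Counts of missed days are usually skewed and differ widely between patients, and only patients in work or school contribute. If a patient's earlier absence predicts later absence, leaving it out keeps that variation in the error and widens the interval for the treatment rate ratio.

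The SAP gives no reason for treating this endpoint differently from WPAI-AD hours missed, which measures nearly the same thing and is adjusted for baseline. Its list of changes (Section 13) even gives the wish to add baseline as a covariate as the reason for moving the EASI responder analysis away from CMH.

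What is at stake is the precision of one exploratory estimate.

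**Working it through.** **1. Is there a planned figure to reproduce?** Not for this endpoint: the documents give no event rate, dispersion, correlation, number of working patients or power. The nearest figure is the 150 evaluable patients for the primary endpoint (protocol 9.2, SAP 4.1). With SD 44, difference 25, 2:1 allocation and 90% power, placebo n = 1.5 × (1.960 + 1.282)² × 44²/25² ≈ 48.8, so 49 placebo and 147 in total, against 150 stated. Below, 150 serves only as a starting count. All other inputs are assumptions.

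**2. Simple approximation.** If baseline and outcome have correlation ρ, adjustment multiplies the variance by 1 − ρ², and power becomes Φ((z + 1.96)/√(1 − ρ²) − 1.96), where z is the normal quantile of the unadjusted power.

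- ρ = 0.3: 70% becomes 74.0%
- ρ = 0.5: 70% becomes 81.8%; 80% becomes 89.9%
- ρ = 0.6: 70% becomes 87.4%

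This is a continuous-outcome formula and is only a guide for counts.

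**3. Negative binomial formula.** Var(log rate ratio) = (1/μ₀ + k)/n₀ + (1/μ₁ + k)/n₁, with dispersion k replaced by k(1 − f) when baseline explains a fraction f of it. Assumed: 60–80% of 150 in work or school, placebo mean μ₀ of 1 to 3 days, k of 2 to 4, rate ratio 0.5.

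One case: n₀ = 40, n₁ = 80, μ₀ = 3, μ₁ = 1.5, k = 2.

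- f = 0: variance = 2.3333/40 + 2.6667/80 = 0.0917, SE 0.303, power Φ(0.693/0.303 − 1.96) = 0.63
- f = 0.25 (k = 1.5): variance = 1.8333/40 + 2.1667/80 = 0.0729, SE 0.270, power 0.73

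Over the whole grid, power without baseline is 0.27 to 0.63. The gain is about 1–4 points at f = 0.05–0.10, 5–10 at f = 0.25 and 13–22 at f = 0.50.

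**4. Simulation with log(baseline count + 0.5) added.** This allows for a noisy baseline count. All settings use 2:1 allocation and rate ratio 0.5.

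| Setting | Link between baseline and outcome | Change in power |
|---|---|---|
| 130 patients, placebo mean 3, 21-day baseline recall, no region term, 400 runs | correlation about 0.25 | 82.8→85.8%, 67.3→71.0% |
| same | about 0.37 | 82.3→90.0% |
| same | about 0.44 | 67.8→76.3% |
| 130 patients, placebo mean 3, 28-day recall, 500 runs | 0.13–0.15 | 0 to +1 point |
| same | 0.26–0.30 | +3 to +5 |
| same | 0.39–0.46 | +6 to +13 |
| 120 patients, placebo mean 2, 28-day recall, region in model, 600 runs | 0–30% of log-rate variance shared | −1 to +1 |
| same | 60% shared | 67.0→70.7% (k = 2), 56.0→62.6% (k = 4) |

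Simulation error is about 2 points per power figure in the last setting. The simulated gains are mostly 0 to 8 points and pass 5 only above a correlation of roughly 0.35.

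**5. Can the covariate be computed?** The missed-days form (protocol Appendix 9) asks for days missed since the previous assessment. Nothing earlier than Week 0 is scheduled for this question, so the Week 0 recall window has no fixed length and a per-week rate has no denominator. The count as reported can be used. SAP 15.8 also provides for patients with no baseline record, so a missing-data rule is needed.

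**The case against.** The strongest reply is that nothing here is an error. A negative binomial count model with a log-duration offset is valid without a baseline term. In a change-score MMRM, adjusting for baseline is close to integral; here it is a choice about precision. The baseline count has an undefined recall window, WPAI-AD hours leave out students, and every power figure is assumed. All of that stands, and it limits the point to a modest suggestion.

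Three stronger readings are tempting, and the documents do not support them.

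- **That the model ignores the stratification factor.** It adjusts for region, and the SAP equates the two: besides 8.1.1, the EASI logistic model in 8.2.8 uses "baseline value of EASI, randomization stratum (region) as fixed effect covariates". PSG sites are in the US only, so at most the PSG/non-PSG split within the US is lost, and 8.1.1 pools that split if PSG enrolment falls below half of plan. Even with an assumed two-fold PSG versus non-PSG rate, splitting it moves power only from 0.464 to 0.469 (k = 3, 40 and 80 patients, mean 2, rate ratio 0.5).
- **That pre-treatment days dilute the rate ratio.** If r days of pre-treatment recall were added to 84 days, a true ratio of 0.5 would become (42 + r)/(84 + r): 0.54, 0.57 or 0.63 for r = 7, 14 or 28. But the endpoint runs from baseline to Week 12, 8.2.20 speaks of 12 weeks, and 15.8 starts the first interval at randomisation and caps the days when no baseline assessment exists. Counting earlier days would contradict the stated endpoint. The missing start needs only a clarifying line.
- **That every other efficacy model adjusts for baseline.** The last EASI fallback in 8.2.8 is CMH by stratum alone.

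**Conclusion.** The point holds as a small, inexpensive gain in precision. The 8.2.20 model leaves out any baseline measure of missed work although two are collected, and the closest comparable endpoint is adjusted. The size cannot be derived from the documents. It depends on how well a noisy Week 0 count predicts later absence: with a weak link there is no gain, and the 13-point top of the simulated range needs the highest correlations assumed. These figures are illustrations and should not be quoted as this trial's power loss. With a log link, adding the covariate does not change what the rate ratio means, provided the effect does not vary with baseline. The endpoint is exploratory, unpowered and reported at nominal level, so no confirmatory conclusion changes.

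**What to change.** - **SAP 8.2.20, text and GENMOD call:** keep treatment, region and the offset, and add one baseline covariate chosen in advance. Use either log(baseline missed days as reported + 0.5), not a per-week rate, or baseline WPAI-AD hours missed due to AD.
- **Missing baseline:** add a missing-baseline indicator with a fixed fill-in value, so that patients without a record stay in the model. If WPAI-AD hours are chosen, it also keeps students in.
- **SAP 15.8:** state that the missed-days sum starts after the baseline visit, so that days reported at Week 0 enter only as the covariate.

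The cost is a few lines of SAP text, two model terms and a missing-baseline rule; no new data are needed. The downside is a noisy covariate that may add little. SAP Section 1 allows revisions before database lock; after lock, the adjusted model should be reported as a labelled sensitivity analysis.
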